#### 4.6 Eligibility Criteria

Study staff must adhere to MCWCC CTO SOPs regarding eligibility review/confirmation.

No waivers of protocol eligibility will be granted. When clinical factors relating to an eligibility item are unclear or questionable, the study PI ([name], [contact]) can only provide guidance or clarification on eligibility.

#### **Inclusion Criteria**

Each subject must meet all the following inclusion criteria to be enrolled in the studv:

- 1. Diagnosis of multiple myeloma with measurable disease (at the time of diagnosis: serum M-protein ≥ 0.5 g/dL or urine M-protein ≥200 mg/24 hour or involved serum-free light chain >10 mg/dL provided that the ratio of involved/uninvolved light chain is abnormal). Patients with no biochemically measurable disease may be enrolled if bidirectionally measurable plasmacytomas or bone marrow plasmacytomas >10% are present prior to CAR-T infusion (sites must explicitly identify these patients to the MCW Multisite Team upon enrollment, as only four of these patients will be permitted on study, after which no future patients will be permitted to be enrolled).
- Received at least four prior lines of therapy (including a PI, IMiD, and anti-CD38 monoclonal antibody – note radiation therapy is considered a line of therapy) given before anti-BCMA CAR-T cell therapy, and has not progressed/relapsed after receiving CAR-T therapy.
- Achieved at least SD to CAR-T therapy and remained progression-free after anti-BCMA CAR-T administration until enrollment (this requirement is also necessary prior administration of first study drug).
- Voluntary consent (per sIRB requirements) must be given before performance of any study-related procedure not part of standard medical care, with the understanding that consent may be withdrawn by the subject at any time without prejudice to future medical care.
- 5. Age  $\geq$  18 years.
- Life expectancy  $\geq$  six months.
- 7. Eastern Cooperative Oncology Group (ECOG) performance status 0–2.
- 8. Creatinine clearance (CrCl)  $\geq 30 \text{ mL/min/1.73 m}^2$  (using formula MDRD).
- Adequate hepatic function evidenced by AST and ALT  $\leq$  2.5 x ULN, bilirubin  $\leq$ 9. 1.5 x ULN (isolated bilirubin ≥1.5xULN is acceptable if bilirubin is fractionated and direct bilirubin <35%).
- 10. Adequate bone marrow function evidenced by hemoglobin  $\geq 8$  g/dL, platelets ≥75,000/mm³ (without transfusion of platelets in the prior seven days) and absolute neutrophil count ≥1,500/mm³ (growth factors are allowed during screening, but not within seven days prior to obtaining this result).
- 11. Spot urine (albumin/creatinine ratio) < 500 mg/g (56 mg/mmol) OR urine dipstick negative/trace (if  $\geq$  1+ only eligible if confirmed  $\leq$  500 mg/g (56 mg/mmol) by albumin/creatinine ratio (spot urine from first void).
- 12. Female participants: Contraceptive use by women should be consistent with local regulations regarding the methods of contraception for those participating in clinical studies.

Short Title: MCW EMBRACE TRIAL Version No.: 3 32

Subject Initials:	Subject Study ID:
Enrolling physician signature: _	Date:

A female participant is eligible to participate if she is not pregnant or breastfeeding, and at least one of the following conditions applies:

Is not a woman of childbearing potential (WOCBP). OR

Is a WOCBP and using a contraceptive method that is highly effective (with a failure rate of <1% per year), preferably with low user dependency during the intervention period and for four months after the last dose of belantamab mafodotin and agrees not to donate eggs (ova, oocytes) for the purpose of reproduction during this period. The investigator should evaluate the effectiveness of the contraceptive method in relationship to the first dose of study intervention.

- WOCBP must have a negative highly sensitive serum pregnancy test within 72 hours of dosing on C1D1 and agree to use a highly effective method of contraception during the study and for four months after the last dose of belantamab mafodotin.
- Additional requirements for pregnancy testing during and after study intervention are provided in Appendix 4 and the study calendar (schedule of activities).

#### 13. Male participants:

Contraceptive use by men should be consistent with local regulations regarding the methods of contraception for those participating in clinical studies.

Male participants are eligible to participate if they agree to the following from the time of first dose of study until six months after the last dose of belantamab mafodotin to allow for clearance of any altered sperm:

Refrain from donating sperm.

AND either:

Be abstinent from heterosexual intercourse as their preferred and usual lifestyle (abstinent on a long-term and persistent basis) and agree to remain abstinent.

OR

Must agree to use contraception/barrier as detailed below:

• Agree to use a male condom, even if they have undergone a successful vasectomy and female partner to use an additional highly effective contraceptive method with a failure rate of <1% per year as described in when having sexual intercourse with a WOCBP (including pregnant females).

Subject Initials:	Subject Study ID:	
Enrolling physician signature:	Date:	

#### **Exclusion Criteria**

Patients meeting any of the following exclusion criteria are not to be enrolled in the study:

- 1. Prior exposure to belantamab mafodotin before enrollment on the trial, including before administration of commercial anti-BCMA CAR-T.
- 2. Evidence of progression/relapse after BCMA CAR-T before enrollment (this requirement is also necessary prior to administration of first study drug).
- 3. Subject has achieved CR/sCR at the time of enrollment (this requirement is also necessary prior to administration of first study drug).
- 4. Patient was given BCMA CAR-T under EAP (expanded access protocol) for non-conforming product.
- 5. Subject progressed on a prior anti-BCMA therapy before receiving commercial anti-BCMA CAR-T.
- 6. Any previous treatment-related adverse events higher than grade 1 at enrollment (except for alopecia and grade 2 neuropathy).
- 7. Acute active infection requiring treatment within 14 days of enrollment (this requirement is necessary also prior administration of first study drug).
- 8. Current or prior involvement of central nervous system by multiple myeloma.
- 9. Smoldering multiple myeloma or POEMS.
- 10. Pregnant or lactating females.
- 11. Major surgery or prior treatment with a monoclonal antibody within 30 days prior to enrollment (this requirement is necessary also prior administration of first study drug).
- 12. Evidence of cardiovascular risk including any of the following:
  - a. Evidence of current clinically significant untreated arrhythmias, including clinically significant ECG abnormalities including second-degree (Mobitz Type II) or third-degree atrioventricular (AV) block.
  - b. History of myocardial infarction, acute coronary syndromes (including unstable angina), coronary angioplasty, or stenting or bypass grafting within three months of enrollment.
  - c. Class III or IV heart failure as defined by the New York Heart Association functional classification system (NYHA, 1994)
  - d. Uncontrolled hypertension.
- 13. Nonhematologic malignancy within the past three years with the exception of a) adequately treated basal cell carcinoma, squamous cell skin cancer, or thyroid cancer; b) carcinoma *in situ* of the cervix or breast; c) prostate cancer of Gleason score 6 or less with stable prostate-specific antigen levels; or d) cancer considered cured by surgical resection or unlikely to impact survival during the duration of the study, such as localized transitional cell carcinoma of the bladder or benign tumors of the adrenal or pancreas.
- 14. Participant must not have current corneal epithelial disease except mild changes in corneal epithelium.
- 15. Participant must not have current unstable liver or biliary disease defined by the presence of ascites, encephalopathy, coagulopathy, hypoalbuminemia, esophageal or gastric varices, persistent jaundice, or cirrhosis. **Note:** Stable non-cirrhotic chronic liver disease (including Gilbert's syndrome or asymptomatic gallstones) or hepatobiliary involvement of malignancy is acceptable if otherwise meets entry criteria.
- 16. Participant must not have presence of active renal condition (infection, requirement for dialysis or any other condition that could affect participant's

Subject Initials:	Subject Study ID:
Enrolling physician signature:	Date:
safety). Participants with isolated prot	einuria resulting from MM are eligible,

- provided they fulfil inclusion criteria.
- 17. Participant must not use contact lenses while participating in this study, unless directed by an ophthalmologist.
- 18. Participant must not have used an investigational drug or approved systemic antimyeloma therapy (including systemic steroids) within 14 days or five half-lives, whichever is shorter, preceding enrollment (this requirement is also necessary prior administration of first study drug). Participant must not have received radiation therapy within 14 days of enrollment.
- 19. Participant must not have had plasmapheresis within seven days prior to enrollment (this requirement is also necessary prior administration of first study drug).
- 20. Participant must not have had major surgery ≤ four weeks prior to enrollment (this requirement is also necessary prior administration of first study drug).
- 21. Participant must not have any evidence of active mucosal or internal bleeding.
- 22. Participant must not have known immediate or delayed hypersensitivity reaction or idiosyncratic reactions to belantamab mafodotin or drugs chemically related to belantamab mafodotin, or any of the components of the study treatment.
- 23. Participant must not have known HIV infection (screening test not required), unless the participant can meet all of the following criteria:
  - a. Established anti-retroviral therapy (ART) for at least 4 weeks and HIV viral load <400 copies/mL
  - b. CD4+ T-cell (CD4+) counts ≥350 cells/uL
  - c. No history of AIDS-defining opportunistic infections within the last 12 months
- 24. Participant must not have presence of hepatitis B surface antigen (HBsAg), or hepatitis B core antibody (HBcAb) at screening or within three months prior to first dose of study treatment. Note: presence of hepatitis B surface antibody (HBsAb) indicating previous vaccination will not exclude a participant.
- 25. Participant must not have positive hepatitis C antibody test result or positive hepatitis C RNA test result at screening or within three months prior to first dose of study treatment.
  - **Note**: Participants with positive hepatitis C antibody due to prior resolved disease can be enrolled, only if a confirmatory negative hepatitis C RNA test is obtained. **Note**: Hepatitis RNA testing is optional and participants with negative hepatitis C antibody test are not required to also undergo hepatitis C RNA testing.
- 26. Prior allogenic stem cell transplant within one year before enrollment, or current evidence of GvHD, or on systemic immunosuppressive therapy for GvHD at least six weeks before enrollment. NOTE Participants who have undergone syngeneic transplant will be allowed, only if no history of GvHD
- 27. Symptomatic amyloidosis, active POEMS syndrome (polyneuropathy, organomegaly, endocrinopathy, monoclonal plasma proliferative disorder, skin changes) or active plasma cell leukemia at the time of screening.
- 28. Any serious and/or unstable pre-existing medical, psychiatric disorder or other conditions (including lab abnormalities) that could interfere with participant's safety, obtaining informed consent or compliance to the study procedures.
- 29. Administration of live or live-attenuated vaccines are contraindicated 30 days

Subject Initials: Su	bject Study ID:
Enrolling physician signature:	Date:
prior to the first dose of study treatment. Killed administered; however, the response to such va	

#### 4.7 Discontinuation of Study Treatment, Withdrawal, and Compliance

Discontinuation from the study treatment does not mean discontinuation from the study. Subject will be considered in follow-up, study procedures should still be completed as indicated by the study protocol, and AEs/SAEs will continue to be reported according to this protocol.

It is preferred that in cases of intended discontinuation from study intervention that are not due to adverse events or of immediate subject safety concern participating sites email the MCW Multisite Team prior to the discontinuation to determine if any efforts/actions might be safely taken to continue subject participation.

The MCW Multisite Team should be notified via the MCW Multisite Team email within 24 hours of discontinuation of study intervention, describing the nature of the discontinuation. OnCore® subject status (treatment and follow-up tabs) and discontinuation eCRF should be completed within 24 hours of discontinuation.

In the absence of treatment delays due to adverse events (refer to dose modification section and holds in Section 5), study treatment/intervention may continue until:

- Disease progression.
- General or specific changes in the subject's condition renders the subject unacceptable for further treatment in the investigator's judgment.
- Inter-current illness that prevents further treatment administration.
- Subject decides to withdraw from the study.
- The subject has significant noncompliance with the protocol (see below).
- Unacceptable adverse event(s).
- Study discontinuation or closure.

Subjects who sign the informed consent form and are enrolled but do not receive the study intervention may be replaced. Subjects who sign the informed consent form, enroll and receive the study intervention, but subsequently withdraw, or are withdrawn or discontinued from the study will not be replaced.

#### **Consent Withdrawal**

A subject may decide to withdraw from the study at any time. Sites must follow the sIRB SOPs regarding consent withdrawal.

If a subject intends on withdrawing consent, sites should confirm which of the following options the subject chooses, document the discussion, upload the documentation to shared site study folder and update OnCore®, and email the MCW team email:

- a. Full consent withdrawal, with no study follow-up.
- b. Selective consent withdrawal from interventional portion of the study, but agrees to continued follow-up of associated clinical outcome information.

#### **Investigator-initiated Withdrawal**

The investigator will withdraw a subject whenever continued participation is no longer in the subject's best interests. Reasons for withdrawing a subject include, but are not limited to, disease progression, the occurrence of an adverse event or a concurrent illness, a subject's request to end participation, a subject's noncompliance (see below) or simply significant uncertainty on the part of the investigator that continued

participation is prudent. Sites should notify the MCW Multisite Team (via the MCW Multisite Team email) within 24 hours in such cases. The reason for study withdrawal and the date the subject was removed from the study must be documented in OnCore®.

#### Subject Compliance

The study team should re-educate the subject on the importance of compliance as necessary and document noncompliance. If this is an ongoing issue, then, the MCW PI should be contacted to determine whether the subject should continue on trial.

#### 4.8 Lost to Follow-up

The following actions should be taken if a participant fails to return to the clinic for a required study visit and/or is unable to be reached for follow-up:

- The investigator or designee should make every effort to regain contact and/or reschedule a missed visit with the participant.
- A participant is deemed lost to follow-up if his/her status cannot be obtained after all of the following occurs at two consecutive scheduled protocol calendar time points:
  - Three telephone calls (at least one day apart) from the study team are unanswered.

A letter to the participant's last known mailing address goes unanswered (refer to Appendix 2). Sites may use their own letter but must follow sIRB policies regarding approval.

- These contact attempts should be documented in the participant's medical record or study file.
- Update OnCore® (follow-up tab and eCRF) when a participant is officially considered lost to follow-up.
- If a subject is considered lost to follow-up, but subsequently contacts the participating site study team, the subject should be considered in follow-up again, with subject approval, and the study team must notify the MCW Multisite Team via the MCW Multisite Team email.

#### 4.9 Accrual Suspension and Closure

The MCW Multisite Team facilitates the suspension and closing of accrual in the following manner:

- The MCW Multisite Team sends accrual reports periodically and notifies sites when nearing suspension requirements.
- Sites must inform the MCW Multisite Team (via the MCW Multisite Team email) of any new or potential consents by the end of the business day.
- The MCW Multisite Team will inform participating sites when the actual or potential number of consents equals the number of available enrollment slots, at which time new consenting is suspended.
- If one of the consented subjects (in screening) is ineligible, accrual reopens until a subject is consented to fill that accrual spot.
- If all the consented subjects end up being eligible, the MCW Multisite Team emails an accrual closure notice.

#### 4.10 End of Study Definition

A participant is considered to have completed the study if he or she completed all phases of the study, including the last visit or the last scheduled procedure shown in the calendar of events or has been discontinued.

#### 4.11 Study Discontinuation and Closure

This study may be temporarily suspended or prematurely terminated if there is sufficient reasonable cause (as determined by the MCW Multisite Team, DSMC, drug manufacturers, FDA, and/or sIRB). Written notification documenting the reason for study suspension or termination will be provided by the suspending or terminating party to study participants, investigator, funding agency, the investigational new drug (IND) sponsor and regulatory authorities. If the study is prematurely terminated or suspended, the MCW Principal Investigator (PI) and MCW Multisite Team will promptly inform study sites, the MCW Institutional Review Board (sIRB), and sponsor, and will provide the reason(s) for the termination or suspension. Study participants will be contacted, as applicable, and be informed of changes. Participating sites will adhere to the sIRB policies.

#### **5 TREATMENT PLAN**

#### 5.1 Treatment

Subjects will receive belantamab mafodotin as maintenance therapy. Belantamab mafodotin will be administered IV over approximately 30 minutes at the recommended dose of 1.9 mg/kg IV day 1 of every 56-day cycle (+/- 3 days).

Maintenance therapy with belantamab mafodotin will continue until progressive disease (PD), death, unacceptable toxicity, withdrawal of consent or end of study, whichever occurs first. Dose interruptions or reductions may be required to address potential drug-associated toxicities.

The dose to be administered will be based on actual body weight calculated at baseline (cycle 1 day 1). However, if the change in body weight is greater than 10%, the dose will be recalculated based on the actual body weight at the time of dosing. The dose may be reduced to address toxicity as described in Section 5.2.

Arm	Belantamab mafodotin (Day 1 of every 56-day cycle)	
A	1.9 mg/kg IV over at least 30 minutes	

#### **5.2 Dose Modifications**

#### 5.2.1 Adjustments Due to Body Weight

The actual body weight in kg at baseline (on cycle 1 day 1) will be used for dose calculation of belantamab mafodotin in all subjects during the treatment period. As noted above, if the change of body weight is greater than 10%, the dose should be recalculated based on the actual body weight at the time of dosing.

#### **5.2.2 Dose Reductions for Toxicity**

Permitted dose reductions for belantamab mafodotin are shown in **Table 2**. Belantamab mafodotin-related AEs are summarized in **Table 3**. General dose modification and management guidelines for drug-related AEs not otherwise specified are summarized in **Table 3**. Dose modification guidelines for cornea-related AEs associated with belantamab mafodotin are summarized in **Table 4**.

Table 2. Permitted dose reduction for belantamab mafodotin

Starting dose	First reduction	Additional reduction
1.9 mg/kg	1.4 mg/kg	If dose delays/modifications detailed below do not satisfy the conditions needed to avoid another dose reduction, the subject must be discontinued. Recommend emailing study PI (cc: MCW Multisite Team) prior to this occurring whenever possible.

Only one dose reduction (to 1.4 mg/kg) is permitted from the starting dose of 1.9 mg/kg. If the participant cannot tolerate the drug after the allowed dose reduction of belantamab mafodotin, the participant will permanently discontinue treatment for lack of tolerability. Any dose level below 1.4 mg/kg is not planned. In case of full resolution of symptoms which lead to dose reduction, further treatment at the previous dose level may be considered by the investigator, after consultation with the sponsor-investigator (cc: MCW Multisite Team email).

Dosing delays are permitted in the case of toxicity, medical/surgical events, or for logistical reasons not related to study therapy (e.g., elective surgery, unrelated medical events, subject's vacation/holidays, but not for subject's decision to delay treatment). The reason for any dose delay should be documented in the subject's eCRF and clinic record.

#### Table 3a. Dose modifications

\*Note these toxicities are known to be associated with use of belantamab mafodotin. The following actions should be taken whether or not the toxicity may be attributed to other possible causes.

Toxicity	Grade/description of toxicity	Action
Elevated serum creatinine, which cannot be explained by concomitant sepsis, TLS, other severe condition with fever, or dehydration a	annot be explained by tant sepsis, TLS, vere condition with	
Serum creatinine ≥Grade 3 (compared to baseline)	>3.0 mg/dL from baseline Or 3.0–6.0 X ULN	
 
Provide appropriate medical treatment.
 
Hold treatment with belantamab mafodotin.
 
Discuss with study PI to determine appropriateness of further dosing (cc: MCW Multisite Team email).
 

Spot urine (creatinine/albumin ratio)	>2,000 mg/g (or 224 mg/mmol)	
 
Retest (at least seven days apart).
 
If not confirmed, continue belantamab mafodotin at current dose.
 
If confirmed on retest and no clear evidence of disease progression.
 

Toxicity	Grade/description of toxicity	Action
		
 
○ Interrupt treatment with belantamab mafodotin.
 
○ Repeat testing within four weeks.
 
-If spot urine ≤2,000 mg/g (224 mg/mmol), may restart belantamab mafodotin with one dose-level reduction.
 
- If spot urine remains >2,000 mg/g (224 mg/mmol) after four weeks, permanently discontinue belantamab mafodotin and withdraw participant from study; provide treatment as clinically indicated and follow for resolution.
 

Urine dipstick	2+	May continue belantamab mafodotin dosing.     Confirm by quantitative assessment using albumin/creatinine (spot urine from first void).  If albumin/creatinine ≥2000 mg/g, at the next cycle follow guidance above for spot urine.
	≥ 3+	Interrupt treatment and follow-up for recovery.  Implement quantification of albumin/creatinine ratio.
Thrombocytopenia (on days	Grade 3 (Platelet count 25,000 to less than 50,000/mcL)	No bleeding: continue treatment with one dose-level reduction.     Consider reverting to previous dose once thrombocytopenia recovered to grade 2, or less.     With bleeding: withhold the dose, continue treatment after recovery with one dose-level reduction.     Consider additional supportive treatment (e.g., transfusion), as clinically indicated and per local practice.
of dosing)	Grade 4 (Platelet count less than 25,000/mcL)	
 
Withhold the belantamab mafodotin dose. Consider restarting with one dose-level reduction if recovered to ≤ grade 3, only if there is no active bleeding at time of treatment restart.
 
If thrombocytopenia is considered disease related, is not accompanied by bleeding, and recovers with transfusion to >25 x10^9/L, continuing treatment with dose reduction may be considered after discussion with the sponsor-investigator (cc: MCW Multisite Team email).
 

Febrile neutropenia	Grades 3–4 Defined as: single temperature of 38.3°C, or sustained 38°C for >1 hour AND ANC <1.0×10°/L	
 
Withhold belantamab mafodotin and immediately hospitalize participant with appropriate management, per local institutional guidance.
 
Consider additional supportive treatment per local practice (e.g., growth factors).
 
Upon recovery, consider a 25% dose reduction of belantamab mafodotin, if neutropenia was drug related.
 

Afebrile neutropenia	Grades 3–4 (Defined as ANC <1.0x10  /L)	
 
If noted on day 1 of any cycle, withhold belantamab mafodotin dose.
 
Resume belantamab mafodotin at preheld dose once neutropenia recovers to grade ≤2 (ANC ≥1.0x10^9/L) on day 1 of a subsequent cycle.
 
Prophylactic antibiotics, per physician discretion and local institutional guidance. Consider growth factors.
 
Local guidance must be followed for hematological monitoring if more conservative than the protocol SoA specifications.
 
In cases of frequent recurrent neutropenia (ANC<1.0x109/L), consider dose reduction of belantamab mafodotin.
 

Infusion reaction b	Grade 2	Stop the infusion, provide medical treatment and continue at slower rate after resolution to grade 0–1.

Short Title: MCW EMBRACE TRIAL 41 Version No.: 3
Version Date: 12/29/2022

Toxicity	Grade/description of toxicity	Action	
	Grade 3	Further treatment with belantamab mafodotin needs to be discussed with sponsor-investigator. Continuation only allowed after recovery to ≤grade 1 and with premedication, and extension of infusion time to 2–4 hours. Any future infusion needs to be premedicated.	
	Grade 4	Permanently discontinue.	
	Grade 1	Continue treatment at the full dose when toxicity resolves to grade < 1.	
Pneumonitis	Grade 2	
 
Withhold treatment with belantamab mafodotin.
 
Upon recovery, restart treatment with one dose-level reduction.
 
If patient is already at the lowest dose level (1.4 mg/kg), then rechallenge with the same dose; this must be discussed with the study PI.
 
	
	Grades 3–4	Permanently discontinue treatment with belantamab mafodotin.	
Urine dipstick	2+	
 
May continue belantamab mafodotin dosing.
 
Confirm by quantitative assessment using albumin/creatinine (spot urine from first void).
 
If albumin/creatinine ≥2,000 mg/g, at the next cycle follow guidance above for spot urine.
 
	
	≥3+	Interrupt treatment and follow up for recovery.  Implement quantification of albumin/creatinine ratio.	

<sup>a These criteria do not apply to participants on dialysis.

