#### 4.1 Subject Status

Subject statuses throughout the trial are defined as follows:

- Prescreening: preconsent (subject considering trial or study staff considering patient for the trial per institutional recruitment methods).
- Screening: period after consent, but prior to eligibility confirmation.

Short Title: MCW EMBRACE TRIAL Version No.: 3 Version Date: 12/29/2022

- Consented: consented, prior to eligibility confirmation.
- Eligible: the local investigator confirms all eligibly criteria apply.
- On study/enrolled: date eligibility is confirmed.
- On arm: date of enrollment.
- On treatment: first day treatment was given to the last day treatment was given.
- Off treatment: the last day treatment was given.
- Off arm: the last day treatment was given.
- On follow up: from last day of treatment to the end of follow-up period.
- Off study: follow-up period completed, with no additional data gathered.
- Withdrawn: subject fully withdraws consent (i.e., refuses ALL follow-up, even survival) or is taken off study by the local PI.

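### Table 3a's albuminuria rule takes the participant off study as well as off drug, which conflicts with the protocol's own follow-up rules and leaves endpoint follow-up unclear

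*Combined protocol and SAP*

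**What the plan says.** Table 3a (Section 5.2.2) deals with a spot urine ratio above 2,000 mg/g that is confirmed on retest, without clear evidence of progression, and still above that level after four weeks. The site is to "permanently discontinue belantamab mafodotin and withdraw participant from study". The same sentence goes on: "provide treatment as clinically indicated and follow for resolution".

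The opening of Section 4.7 states the general rule: "Discontinuation from the study treatment does not mean discontinuation from the study". For such a patient, "study procedures should still be completed as indicated by the study protocol, and AEs/SAEs will continue to be reported according to this protocol".

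Further down Section 4.7, the investigator-initiated withdrawal text reads: "Reasons for withdrawing a subject include, but are not limited to, disease progression, the occurrence of an adverse event or a concurrent illness". Section 4.1 defines the status as "Withdrawn: subject fully withdraws consent (i.e., refuses ALL follow-up, even survival) or is taken off study by the local PI". The neighbouring entry is "Off study: follow-up period completed, with no additional data gathered".

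Sections 3.1 and 5.8 keep patients who stop before progression in three-monthly follow-up, and then in survival follow-up. The grade 4 infusion-reaction rule in Section 5.3 removes the patient from study treatment only and moves the patient into follow-up.

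**The concern.** Table 3a gives two instructions: stop the drug, and leave the study. The second is out of line with the protocol's general rule. A site that follows it would give the patient the Withdrawn status and could reasonably stop collecting outcome data.

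These patients are progression-free when the rule applies, so under Section 8.2.1 they would be censored for PFS at the last date known alive without progression. OS would be cut short in the same way, and the 70-day safety visit and later new adverse events could be missed. Section 4.7 does not replace treated subjects who are withdrawn.

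The loss could be related to outcome. Table 3a applies its actions whatever the suspected cause of the toxicity, and exclusion criterion 16 recognises that proteinuria can come from the myeloma itself. Some removals might therefore reflect disease activity. In a single-arm trial of 45 patients tested against a fixed 54%, censoring a few patients shortly before they progress would push the estimate upward.

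Listing progression as a reason for withdrawal raises a separate problem. PFS is safe, because the event has already occurred, but a literal reading would cost OS data that Section 3.1 intends to collect after progression.

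**Working it through.** **1. The texts side by side**

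| Place | Off drug | Off study |
|---|---|---|
| Table 3a, persistent albuminuria | yes | yes; renal event followed to resolution |
| 4.7, opening | yes | no; procedures and AE/SAE reporting continue |
| 3.1 and 5.8 | yes | no; disease and survival follow-up continue |
| 5.3, grade 4 infusion reaction | yes | no; enters follow-up |
| 4.7, investigator-initiated withdrawal | – | allowed for an adverse event or progression |
| 4.1, Withdrawn | – | status covers removal by the local PI; what follow-up remains is not stated |
| 6.2.1 | – | AEs followed to resolution, consent withdrawal or loss to follow-up |

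The other permanent-discontinuation rules in Tables 3a and 4 concern treatment only. The albuminuria rule is the exception.

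**2. Baseline design**

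Inputs are from Sections 8.1 to 8.2.3: N = 45, null 54% (0.40/0.74 = 0.5405), alternative 74%, one-sided 5%, stated power 84%. The plan does not say on which scale the z-test is computed, so a log-log Kaplan-Meier test is assumed here.

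- Exact binomial, rejecting at 31 or more of 45 progression-free: type I error 3.1%, power 83.0%.
- Two-stage simulation (6,000 runs, exponential PFS, accrual of one then two per month, everyone entering at day 90, nine-month window, futility stop at p ≥ 0.54): type I error 3.1%, power 82.8%.

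Both are within about 1 point of the stated 84%. The baseline type I error on this scale is about 3%, not 5%.

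**3. Withdrawal unrelated to outcome**

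In the two-stage simulation, with withdrawal at a random time in the window:

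- 5% of patients withdrawn: type I error 4.0%, power 83.9%.
- 10% withdrawn: type I error 4.0%, power 84.4%.

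Single-stage, two patients withdrawn at random: about 4%. None of these exceeds the planned 5%. The 10% figure (4.5 of 45 patients) is also the upper limit of the censoring that Section 8.2.3 says was simulated.

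**4. Assumed worst case**

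Exactly k patients who would have progressed are censored just before the event (single-stage log-log test, true rate 54%, 20,000 runs):

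| k | Mean KM estimate | Type I error |
|---|---|---|
| 0 | 0.540 | 3.0% |
| 1 | 0.556 | 5.9% |
| 2 | 0.573 | 9.9% |
| 3 | 0.591 | 15.5% |

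The rise is (0.591 − 0.540)/3 = 0.017, or about 1.7 points per patient.

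**5. Cross-checks**

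- *Rise in the estimate.* A patient censored when the curve stands at S passes on weight 1/45, of which a share 0.54/S reaches month 12. Averaging over S from 1 to 0.54 gives 0.54 × ln(1/0.54)/0.46 = 0.54 × 0.616/0.46 = 0.72. Then 0.72/45 = 0.016, which matches the step from k = 0 to k = 1.
- *Type I error.* Counting each removed progressor as a full success lowers the binomial cut from 31 to 30, 29 or 28, with exact type I error 5.9%, 10.4% and 16.9%. The simulated figures are equal to or a little below these, as expected, because each removal earns less than a full success.
- *Two-stage design.* If 5% or 10% of patients are flagged and only the would-be progressors among them are censored, the expected numbers are 45 × 0.05 × 0.46 = 1.0 and 45 × 0.10 × 0.46 = 2.1. The simulated type I errors are 5.8% and 10.5%, in line with k = 1 and k = 2.

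**The case against.** The strongest reply is that the rest of the protocol already protects these patients. Section 3.1 continues disease evaluations for all subjects, and Section 5.8 follows all patients for survival. Neither lists removal by the investigator as a stopping point. Section 6.2.1 collects adverse events to 70 days after the last dose and follows them to resolution, including in those who discontinue early. On that reading Table 3a is loose wording. This stands in part: the documents are ambiguous and do not plainly order that follow-up end. It does not remove the conflict, because a site still has to choose between two instructions.

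Three stronger readings are tempting, and the documents do not support them.

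- *Safety follow-up ends.* The Table 3a sentence itself requires the renal event to be followed to resolution. What is at risk is the 70-day visit and new events.
- *Section 4.1 puts a patient removed by the local PI among those who refuse even survival contact.* The parenthesis about refusing all follow-up explains full withdrawal of consent only. The two routes share a status label. The text does not say what follow-up the second one keeps.
- *Table 3a contradicts Section 4.7 as a whole.* It conflicts with the opening paragraph but agrees with the investigator-initiated withdrawal text, which allows removal for an adverse event. Section 4.7 points both ways.

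It is also fair to say that the event may be rare, that the documents give no rate, and that nothing in them shows these patients are likelier to progress.

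**Conclusion.** The wording is wrong as written, and of minor priority. Table 3a's instruction to take the participant off study conflicts with the opening of Section 4.7, with Sections 3.1 and 5.8, and with the infusion-reaction rule in Section 5.3. Sections 4.1 and 4.7 do not settle whether such patients stay in follow-up.

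The effect on the primary test depends on two unknowns: how many patients meet the rule, and whether their removal is related to impending progression. If unrelated, type I error is about 4% and no harm follows. If one, two or three of 45 were about to progress and all their later follow-up is lost, it is about 6%, 10% or 16%, against a baseline of about 3% and a plan of 5%. These are assumed worst cases on a log-log, single-stage test. A reader might infer that the trial's false-positive rate will double; the documents give no basis for expecting that. No design figure changes.

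**What to change.** Leave the albuminuria threshold and the treatment-stopping rule untouched. No view is taken on either.

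1. In Table 3a, replace the words that take the participant off study with entry into follow-up under Section 5.8, modelled on the infusion-reaction rule in Section 5.3. This brings it into line with the opening of Section 4.7 and with Section 3.1.
2. In the investigator-initiated withdrawal text of Section 4.7 and the status list of Section 4.1, separate stopping study treatment from leaving the study. State that a subject taken off treatment by the investigator stays in PFS, safety and survival follow-up unless consent to that follow-up is withdrawn.
3. Keep the investigator's ability to act in the subject's best interests. Restricting all study withdrawal to full withdrawal of consent would go further than this point requires.

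The cost is a few words in three places. Sample size stays at 45 and power at about 83 to 84%. Outcome data not collected after a literal reading of Table 3a may not be recoverable.
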